Exclusion Criteria: Study candidates with the following will be excluded: 1) known genitourinary pathology beyond neuropathic bladder (i.e., vesicoureteral reflux, bladder or kidney stones, etc.); 2) use of prophylactic antibiotics; 3) instillation of other intravesicular agents to reduce urinary symptoms or UTI (i.e., gentamycin); 4) psychologic or psychiatric conditions influencing the ability to follow instructions; 5) participation in another study in which results would be confounded; 6) pregnant or breastfeeding women; 7) individuals with a history of acquired or genetic immunodeficiencies; active, acute or chronic serious infections (e.g., viral hepatitis, HIV/AIDs); 8) individuals with cancer/autoimmune disorders; 9) serious allergy to any component or excipients in the live bacterial combination product; 10) no change in neurologic status in the previous 2 weeks; 11) taken antibiotic for any reason in the previous 2 weeks; 12) any patient with history of sensitivity or allergy to ampicillin or tetracycline; and 13) current urinary tract infection or urinary tract infection within the previous 2 weeks; (as defined by Infectious Diseases Society of America CAUTI Guidelines, 2010. According to the Infectious Disease Society of America Guidelines for Diagnosis of Catheter-Associated UTI, the presence of the following urinary symptoms is required for UTI diagnosis in patients using intermittent catheterization: new onset or worsening fever, rigors, altered mental status, malaise, lethargy with no other identified cause, flank pain, costovertebral angle tenderness, acute hematuria, pelvic discomfort, increased spasticity, autonomic dysreflexia or sense of unease. The Guidelines specifically state that “the presence or absence of odor or cloudy urine should NOT be used as an indication for urine culture or antimicrobial therapy” and “the presence, absence or degree of pyuria should NOT be interpreted as an indication for antimicrobial treatment.” If a subject presents with any of these symptoms and there are $\geq 10^3$ cfu/hpf bacterial growth on urine culture, the subject will be excluded and treated for a UTI according to clinical best practice.

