Exclusion Criteria: Study candidates with the following will be excluded: 1) known genitourinary pathology beyond neuropathic bladder (i.e., vesicoureteral reflux, bladder or kidney stones, etc.); 2) use of prophylactic antibiotics; 3) instillation of intravesicular agents to reduce UTI (i.e., gentamycin); 4) psychologic or psychiatric conditions influencing the ability to follow instructions; 5) participation in another study in which results would be confounded; 6) pregnant or breastfeeding; 7) individuals with a history of acquired or genetic immunodeficiencies; active, acute or chronic serious infections (i.g., viral hepatitis, HIV/AIDs); 8) individuals with cancer/autoimmune disorders; 9) serious allergy to any component or excipients in the live bacterial combination product; 10) no change in neurologic status in the previous 2 weeks; 11) taken antibiotic for any reason in the previous 2 weeks; 12) any patient with history of sensitivity or allergy to ampicillin or tetracycline; and 13) current urinary tract infection or urinary tract infection within the previous 2 weeks (as defined by Infectious Diseases Society of America CAUTI Guidelines, 2010. According to the Infectious Disease Society of America Guidelines for Diagnosis of Catheter-Associated UTI, the presence of the following urinary symptoms is required for UTI diagnosis in patients using intermittent catheterization: new onset or worsening fever, rigors, altered mental status, malaise, lethargy with no other identified cause, flank pain, costovertebral angle tenderness, acute hematuria, pelvic discomfort, increased spasticity, autonomic dysreflexia or sense of unease. The Guidelines specifically state that “the presence or absence of odorous or cloudy urine should NOT be used as an indication for urine culture or antimicrobial therapy” and “the presence, absence or degree of pyuria should NOT be interpreted as an indication for antimicrobial treatment.” If a subject presents with any of these symptoms and there are $\geq 10^3$ cfu/hpf bacterial growth on urine culture, the subject will be excluded and treated for a UTI according to clinical best practice.

Baseline Data Collection: After consent, participants will complete the Health History Questionnaire. Thereafter, participants will complete the Urinary Symptom Questionnaire (USQ-NB) weekly.

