Intervention: After 6 months of baseline data collection, participants will receive the *Lactobacillus* (Culturelle) kits. Participants will be instructed on preparation and intravesicular instillation of the *Lactobacillus*, and will have a tutorial with a fellow consumer on use of the patient-initiated SMP_{PRO}. Participants will receive 10 Culturelle tablets the beginning of the

The Impact of Self-Management with Probiotics on Urinary Symptoms and the Urine Microbiome in Individuals with Spinal Cord Injury and Spina Bifida Protocol

5/18/2017

Page 5 of 17

treatment phase. At the end of each week, the coordinator or RA will ask how many remaining tablets the participant has and will instruct them to complete the USQ-NB weekly. If/when urinary symptoms occur, they will be instructed to follow the SMP_{PRO} protocol to determine whether to initiate intravesicular *Lactobacillus* instillation or to seek medical attention. The self-management protocol will also direct them to discontinue *Lactobacillus* instillation or to seek medical attention if symptoms remit, persist or worsen. If participants are directed by the self-management protocol to seek medical attention or s/he feels the need for medical evaluation, s/he will be advised to obtain care as they typically would by their health care provider. Participants will be supplied with letters to be brought to their health care provider notifying them of the study and requesting sharing of urinalysis and urine culture results with the research team. A verified UTI will include those that resulted in antibiotic treatment prescribed by a health care professional.

For the intravesicular *Lactobacillus* instillation, the contents of 1 *Lactobacillus* capsule will be mixed into 45 cc sterile 0.9% saline (adult bladder volume is 450cc, representing 10% of adult bladder volume). After mixing, study participants will draw up the 45 cc of the liquid *Lactobacillus* mixture into a 60cc catheter tip syringe and instill via the intermittent catheter using sterile technique. For children volume is based on age (see table on page 4 of protocol).

Study participant will recheck symptoms after 24 hrs (valid range 22-30 hrs) following the SMP_{PRO} protocol and either perform another *Lactobacillus* instillation or seek medical attention, per the subjects choice. If symptoms still persist 4 hrs after second instillation, study participants are instructed to seek medical attention.

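### Phase II releases Lactobacillus kits for home instillation six months after entry, and the protocol text describes no re-check of exclusions that may have arisen since

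*Combined protocol and SAP*

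**What the plan says.** **Entry.** The Phase II Exclusion Criteria open with "Study candidates with the following will be excluded: 1) known genitourinary pathology beyond neuropathic bladder". The list goes on to "4) psychologic or psychiatric conditions influencing the ability to follow instructions", then "6) pregnant or breastfeeding; 7) individuals with a history of acquired or genetic immunodeficiencies", cancer or autoimmune disorders (8), serious allergy to the product (9), and "12) any patient with history of sensitivity or allergy to ampicillin or tetracycline". The wording addresses candidates, that is, people being screened.

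**Run-in.** After consent, participants complete the Health History Questionnaire and then the weekly USQ-NB for six months of usual care. Phase II uses no study urinalysis or culture.

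**Kit release.** "After 6 months of baseline data collection, participants will receive the" kits. They are taught how to prepare and instil the product and "will have a tutorial with a fellow consumer on use of the patient-initiated" SMP_PRO. Ten tablets are supplied at the start of the treatment phase.

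**Treatment phase.** "At the end of each week, the coordinator or RA will ask how many remaining tablets the participant has", together with a reminder to complete the USQ-NB. Symptoms lead the participant to the SMP_PRO, which directs instillation or medical care. If symptoms persist after a second instillation, the participant is told to seek care.

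**Phase III.** All participants must be enrolled in Phase II. A urine sample is given before the intervention starts, and sampling is up to monthly in the first year, with up to 18 samples in total.

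**The concern.** In many trials dosing follows screening within days, so entry criteria also serve as dosing criteria. Here the design separates them. First possible use falls about 26 to 52 weeks after screening, and several of the listed conditions can begin in that interval and not resolve. A participant who becomes pregnant or receives a cancer diagnosis in month 4 would, on the text as written, still be sent the kit.

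Phase I offers no reassurance for such people. Phase Ia excluded the same conditions ("6) pregnant or breastfeeding women; 7) individuals with a history of acquired or genetic immunodeficiencies", and the others). Phases Ia and Ib planned five adults and five children, each given one dose by study staff with 30 minutes of observation. Phase II supplies ten tablets of a live-organism product for use without that observation. What is at stake is avoidable exposure of a small number of people who now meet the protocol's own exclusions.

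**Working it through.** This is mainly a reading check, because the plan states no figure on this point.

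**Step 1. Which described contacts could detect a new exclusion before instillation?**

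| Contact | What it collects | Decision to withhold or stop for a new exclusion? |
|---|---|---|
| Health History Questionnaire | Taken after consent. Demographic and family items at baseline only. Genitourinary history might be repeated, but no time point is given | None described |
| Weekly USQ-NB | Urinary symptoms | None described for non-urinary conditions |
| Kit instruction and peer tutorial | How to prepare, instil and use the SMP_PRO | None described |
| Weekly staff contact | Tablet count, USQ-NB reminder | None described |
| SMP_PRO, as summarised | Urinary symptoms: instil, stop or seek care | Acts on symptoms only |
| Phase III urine samples | Urinalysis, culture, sequencing. No pregnancy test among the listed items | No result tied to kit use |
| Adverse event record retrieval, DSMB reports | Histories, concomitant medication | Come after an event |

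No row covers pregnancy, immunodeficiency, cancer or a new allergy before exposure.

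**Step 2. Which exclusions belong in a re-check?** Exclusions 1, 4, 6 to 9 and 12 can arise during the run-in and persist. The two-week UTI and antibiotic windows do not belong. Use is triggered by symptoms, so reapplying them would conflict with the intervention.

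**Step 3. How many people might be affected?** The documents give no incidence. Assume a combined rate i of 1% to 5% per year for all the listed conditions, with N = 120 (the Phase II recruitment ceiling).

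- Expected newly ineligible by time T: N × (1 − exp(−i × T)).
- At kit release (T = 0.5 year): 120 × (1 − exp(−0.005)) = 0.60, and 120 × (1 − exp(−0.025)) = 2.96.
- By month 12 (T = 1 year): 120 × (1 − exp(−0.01)) = 1.19, and 120 × (1 − exp(−0.05)) = 5.85.
- Chance of at least one at kit release: 1 − exp(−N × i × T) = 1 − exp(−0.6) = 45%, and 1 − exp(−3.0) = 95%.
- With the 100 participants the power section hopes to retain, the kit-release counts become 100 × (1 − exp(−0.005)) = 0.50 and 100 × (1 − exp(−0.025)) = 2.47.

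These figures count people who have become ineligible. The number exposed is this count times the fraction who then have symptoms, are directed to instil, and do so. The documents do not give that fraction. It lies between 0 and 1, so the counts are upper limits on exposure under each assumed rate.

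**The case against.** The strongest objection is that this argues from silence. The SMP_PRO decision tree governs every use, and neither it nor the kit instructions nor the consent pages are in the supplied text. A reader might infer that the trial has no safeguard. The documents do not support that. They show only that the protocol body describes none.

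The plan also has features that narrow the gap. Participants receive letters telling their health care provider about the study. No more than two instillations per episode are envisaged before medical care. The instruction at kit release is an occasion on which loss of ability to follow instructions might be noticed. These points stand as mitigation, but none is a check for pregnancy, cancer, immunodeficiency or allergy.

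A reader might also take Phase III to share the same unsupervised exposure with nothing but one extra urine sample. That goes too far. Sampling is up to monthly in year 1, often with staff contact. The Phase III Intervention section has study personnel drawing up the dose, while also mentioning treatment at home, so the degree of supervision is unclear. What remains is that no urine result is linked to kit use.

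Exclusion 12 is absent from the Phase Ib list, so the plan does not apply it uniformly. The plan gives no reason for any exclusion, and calling these safety exclusions is an interpretation.

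Finally, a reader might infer that the missing re-check biases the before-after comparison, for example through newly started prophylactic antibiotics. The documents give no rate, effect or timing for this, and a safety re-check would neither cause nor remove such bias. It is not part of this point.

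**Conclusion.** The point holds as a gap in the protocol text. Exclusions are applied at entry, kits are released six months later for home use, and no re-check of newly arisen, persistent exclusions is described. The size is unknown. Under an assumed 1% to 5% per year and 120 participants, about 0.6 to 3 people would be newly ineligible at kit release, with fewer actually instilling. Those figures rest wholly on the assumed rate, on full retention to month 6, and on treating the listed conditions as one combined hazard. They do not estimate harm.

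The conclusion also depends on the unseen SMP_PRO tree and consent pages. If a check is already there, the remedy is a cross-reference. This is a cheap improvement to participant safety. It does not call the design, the sample size or the primary analysis into question.

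**What to change.** In the Phase II Intervention section, add that before kit release the coordinator repeats exclusions 1, 4, 6 to 9 and 12 by phone or online link, refers any positive answer to the investigator, and withholds the kit if an exclusion is confirmed. Because every Phase III participant is in Phase II, one check serves both. At kit release, tell participants to stop instilling and report if such a condition arises later. A brief prompt in the existing weekly contact is optional: over about 26 weeks it would mean up to 120 × 26 = 3,120 extra responses.

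Do not reapply the two-week UTI and antibiotic windows. Keep everyone, including those whose kit is withheld, in weekly USQ-NB follow-up and in the primary analysis.

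The cost is one short checklist per participant and some investigator time for positive answers. A few participants would not be exposed, which slightly dilutes the estimated effect. If 3 of 120 were withheld and would otherwise have had the average benefit, the planned reduction of 1.25 UTIs would become 1.25 × (1 − 3/120) = 1.22, and the reduction of 5 USQ-NB items would become 5 × (1 − 3/120) = 4.88.

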Post-Intervention Follow-Up: After completion of the 6-month patient-initiated self-management protocol intervention period, participants will monitor symptoms weekly using the USQ-NB.

Measurements:

Health History Questionnaire: After subjects give consent, a brief medical history will be conducted using a structured questionnaire, to obtain demographic information and relevant family history (these items will be collected only at baseline), and genitourinary history

Urinary Symptom Questionnaire (USQ-NB): A preliminary urinary symptom questionnaire has been developed with consumer input based on the most common typical and SCI/MS-specific urinary symptoms. The final version (developed in Specific Aim 1 IRB # 2014-187) will be used in this phase of the study. USQ-NB will be completed weekly. All participants will receive a link to the questionnaire every Sunday morning. If they have not responded by Monday morning, they will receive another link. If they have not responded by Tuesday, the study participant will receive a phone call. If there is no response by noon Wednesday, it is considered a missed event.

Patient satisfaction: We have developed a simple four item patient satisfaction “survey” that will be requested at the end of each timeframe. Participants will be asked to rate their satisfaction, thinking only about the preceding time period, with changes in the *frequency* of their symptoms; the amelioration of the *severity* of their symptoms; and changes in the *impact* of their symptoms. A 5-point Likert scale will be used for each of these items (not at all satisfied; not very satisfied; no perceived difference; satisfied; and very satisfied). A fourth item, “Can you estimate, using a scale from 0% <would absolutely never do this>, through 50% <might do this> to 100% <would absolutely always do this>, whether or not you would seek this intervention out and pay for it yourself if insurance did not pay for it”.

Medical Information:

The Impact of Self-Management with Probiotics on Urinary Symptoms and the Urine Microbiome in Individuals with Spinal Cord Injury and Spina Bifida Protocol

5/18/2017

Page 6 of 17

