H1. Compared with usual management, self-management of urinary symptoms with probiotics will reduce the frequency, severity and impact of urinary symptoms and UTIs (PRIMARY OUTCOMES). The goal of aim 2 is to assess the effect of *Lactobacillus* supplementation on the frequency, severity and impact of urinary symptoms and UTIs. This aim can be evaluated with all 100 participants in the SMP pilot study. We expect to find a significant difference in these primary outcomes between our three experimental timeframes (6 months prior to intervention, 6 months of SMP_{PRO} intervention, and 6 month follow-up period). Frequency of UTI will be defined as the number of verified UTIs occurring during the timeframe. Urinary symptoms will be assessed using the USQ-NB where frequency of symptoms, degree of severity, and impact on the individual, will be considered.

We will estimate the average number of symptoms on the USQ-NB endorsed (irrespective of frequency, severity and impact) across the weeks during that time frame, for each participant. Thus, each participant will have a continuous outcome (average number of USQ-NB items endorsed). We will also compute the number of verified UTIs experienced by each participant. These two outcomes are the primary outcomes for our study and analysis; they depend solely on the face validity of the USQ-NB, and on clinically verified UTIs, and so will not be affected by a failure to find or establish formal measurement properties for the USQ-NB, should any occur. They will also be less subject to any variability in participant perceptions of frequency, severity or impact, which can complicate analytic assumptions and limit power and interpretability of change that might be perceived. We will describe these features of the sample over time but will not conduct inference tests on these ratings.

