We propose linear mixed-effects modeling to explore the effect of introduction to/use of the SMP_{PRO} on the number of USQ-NB symptoms (averaged over the entire time frame) and the incidence of UTIs. Each model will include gender as a fixed effect, and time (baseline; SMP_{PRO} use; post-SMP_{PRO} observation) as the explanatory variable, and random effects for intercept (subject) only. This method allows for missing data and the inclusion of covariates where appropriate; however we plan post-hoc analyses of the modeling in order to pinpoint potential interaction effects (e.g., between age or sex and time). The focus of the analyses is to determine whether (irrespective of individual starting values or specific slopes) mean USQ-NB item endorsement and UTI counts go down in the SMP_{PRO} time frame relative to the baseline values (generally negative associations in each regression between the outcome and time) and whether these values stay flat (zero slope), continue to decrease (negative slope) or increase (positive slope) during the post-SMP_{PRO} follow up.

Power calculation: We plan to use mixed effects regression modeling for the most precision in our estimated effects of the SMP_{PRO} on the USQ-NB symptom rate and UTI rate. However, it is difficult to predict the exact form of the final models since our understanding of the USQ-NB symptom makeup, and the univariate associations between gender or age (or any other of the demographic variables we will collect) and these two outcomes. Therefore, for the most conservative estimates, we use the most basic analytic method to estimate the worst-case scenario power calculation, a t-test. In this pair of primary outcomes, alpha is set at 0.025 for each power calculation (and for each inference test). We will have data from 100 participants; however, to protect against a possible 20% drop out rate over the course of the 18-month study, we will recruit 120 persons for this arm, hoping for a final N of 100. If we observe an average of 25 items on the USQ-NB endorsed over the baseline period, then with alpha = 0.025 we would have 81% power to detect a reduction in this average number of items endorsed as low as five

The Impact of Self-Management with Probiotics on Urinary Symptoms and the Urine Microbiome in Individuals with Spinal Cord Injury and Spina Bifida Protocol
5/18/2017

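### An extra weekly staff instruction to complete the USQ-NB is described for the intervention period only, and the symptom co-primary is a period average with no rule for missed weeks, so its intervention mean can shift without any change in symptoms

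*Combined protocol and SAP*

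**What the plan says.** **Prompting common to all periods.** Under Measurements (Phase II), every participant gets a Sunday link and, if needed, a second link on Monday. Then: "If they have not responded by Tuesday, the study participant will receive a phone call". Finally: "If there is no response by noon Wednesday, it is considered a missed event".

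**Baseline.** After the health history, "Thereafter, participants will complete the Urinary Symptom Questionnaire (USQ-NB) weekly". No weekly staff contact is described.

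**Intervention.** A staff contact is added at each week's end: "the coordinator or RA will ask how many remaining tablets the participant has and will instruct them to complete the USQ-NB weekly". This contact does not depend on whether the participant has already answered.

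**Follow-up.** After the intervention period, "participants will monitor symptoms weekly using the USQ-NB". Again no weekly staff contact is described.

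**Outcome and analysis.** Under H1, the symptom co-primary is the average number of items endorsed "across the weeks during that time frame, for each participant". The mixed model estimates the effect of the programme "on the number of USQ-NB symptoms (averaged over the entire time frame) and the incidence of UTIs". On missing data the plan says only: "This method allows for missing data and the inclusion of covariates where appropriate". It gives no imputation rule, minimum number of completed weeks or weighting for missed weeks within a period.

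**Monitoring.** The Data and Safety Monitoring Plan has completion, with and without staff reminders, reported to the DSMB. It does not link that report to the H1 analysis.

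**The concern.** There is no concurrent control group. Each participant is compared with him- or herself across three consecutive periods, so H1 relies on symptoms being measured the same way in each. As written, the prompting changes when the intervention starts and changes back when it ends.

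A higher response rate does no harm in itself. The difficulty arises if response depends on symptoms. If people skip quiet weeks, an added prompt brings more quiet weeks into the intervention average, which falls with no benefit. If people skip weeks when they are ill, the prompt brings in more bad weeks and hides part of a real benefit.

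The plan's remark on missing data does not settle this. A mixed model with three values per participant can use someone who lacks a whole period. It cannot recover weeks already absent from an average that it receives as complete.

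**Working it through.** **Inputs from the documents (Power calculation under H1).** Baseline mean 25 items, reduction 5, SD 16, N = 100, alpha 0.025 for each co-primary, stated power 81%. The plan does not say whether the test is one- or two-sided.

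**1. Reproduce the plan's figure.** Take 16 as the SD of the within-person change and use a two-sided test.
- SE = 16/√100 = 1.6; critical value z(0.9875) = 2.241.
- Power = Φ(5/1.6 − 2.241) = Φ(0.884) = 81.2%, which agrees with 81%.
- A one-sided paired test gives 87.8%, and a two-sample test with 100 per group gives 48.7%, so the paired two-sided reading is used below. With no shift, the chance of a significant result in favour of the intervention is then 1.25%.

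**2. Assumptions.** The documents give no response rates and no week-to-week spread. All of the following are assumed:
- Half of weeks are symptomatic and half quiet. The true mean is 25 in every period, with either 30 and 20 items or 35 and 15 items in the two kinds of week.
- Baseline response is 85% in symptomatic weeks and 70% in quiet weeks. Intervention response is 95% in both.
- A missed week is left out of the average.

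**3. Formula.** With equal shares of the two kinds of week, S and Q items, and response rates r1 and r0:

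reported mean = (r1·S + r0·Q)/(r1 + r0)

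Equal response gives (S + Q)/2 = 25, so the intervention mean is 25.00.

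**4. False fall.** False-benefit probability = Φ(shift/1.6 − 2.241).

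| Items (symptomatic/quiet) | Baseline reads | False fall | False-benefit probability |
|---|---|---|---|
| 30/20 | (0.85×30 + 0.70×20)/1.55 = 39.50/1.55 = 25.48 | 0.48 | Φ(0.302 − 2.241) = 2.6% |
| 35/15 | (0.85×35 + 0.70×15)/1.55 = 40.25/1.55 = 25.97 | 0.97 | Φ(0.605 − 2.241) = 5.1% |

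**5. Sensitivity to the assumptions.**
- Response unrelated to symptoms, for example 70% in all weeks at baseline and 95% in all weeks during intervention: shift 0.00.
- Smaller gain from the prompt (35/15, intervention response 90% and 80%): the intervention mean reads (0.90×35 + 0.80×15)/1.70 = 25.59. The false fall is 25.97 − 25.59 = 0.38, with false-benefit probability 2.3%.
- Reverse pattern (baseline 70% symptomatic, 85% quiet): baseline reads 24.52 (30/20) or 24.03 (35/15), a false rise of 0.48 or 0.97. A true 5-item fall would appear as 4.52 or 4.03, and power would drop to Φ(4.52/1.6 − 2.241) = 72% or Φ(4.03/1.6 − 2.241) = 61%.
- Extreme case, zero items in quiet weeks and a reported baseline mean of 25: the symptomatic share of reported weeks is 0.85/1.55 = 0.548 at baseline and 0.500 during intervention. The shift is 25 × (0.500/0.548 − 1) = −2.2 items. This needs about 25/0.548 = 46 items in every symptomatic week.

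**The case against.** **The asymmetry rests partly on silence.** The baseline and follow-up sections are very short, and a tablet count is possible only once tablets have been supplied. The weekly contact might also overlap in practice with the Sunday link or the Tuesday call. This stands as a caution. But the call goes only to those who have not answered, whereas the tablet contact goes to everyone and carries its own instruction. As written, it is an additional prompt.

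**The common sequence may already keep response high.** Two links and a phone call apply in every period, which could leave little room for a further effect. That is fair, and the documents have no figures to settle it. Reporting completion to the DSMB would make a difference in response visible, but would not correct the comparison.

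**Stronger readings that the documents do not support.**
- A reader might infer that missed weeks are dropped by rule. That is the natural reading of an average over weeks, but the plan only labels them as missed. The firm finding is that no rule is given.
- A reader might infer that all three means come from different response processes. As described, baseline and follow-up share one, so the prompt does not distort the contrast between those two periods. Only contrasts with the intervention mean are exposed.
- A reader might infer that nearly half of the planned effect could be an artefact, from 2.2/5 = 44%. That needs zero items in all quiet weeks, for which the documents offer no support.

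**Conclusion.** The point holds as a described difference in measurement between periods, together with a missing rule for missed weeks in a co-primary outcome. The intervention mean can shift against baseline and follow-up with no true change, and a model fitted to period averages cannot undo that.

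The documents do not show that it will shift, or in which direction. With the assumed response rates and moderate item splits, the false fall is about 0.5 to 1.0 items, or 10% to 19% of the planned 5. The false-benefit probability is then about 3% to 5% against 1.25%. The reverse response pattern would hide benefit by the same amounts. These sizes rest on assumed response rates, assumed item splits, the omission of missed weeks from the average, and 16 as the SD of the within-person change. A change should be made because unequal prompting cannot be corrected once the data are collected and prevention is cheap.

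**What to change.** **Make USQ-NB prompting the same in months 0-18.** Either:
- use the same weekly staff contact and USQ-NB script in all three periods, without the tablet question where no tablets are held; or
- collect the tablet count inside the weekly online questionnaire and drop the separate instruction, so that only the common reminder sequence prompts completion.

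Deleting the instruction but keeping the weekly tablet contact is not enough, because the contact itself acts as a prompt in one period only.

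**In the analysis plan:**
- State how missed weeks enter the period average.
- Add a supporting H1 symptom model fitted to the weekly counts, with a participant random effect and period as a factor. This uses every completed week directly, but does not remove bias when response depends on that same week's symptoms. Equal prompting therefore remains the main remedy.
- Report completion by period alongside the H1 result.

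A sensitivity analysis limited to responses given without staff contact should not be used. As the plan stands, every intervention week includes such contact, so that period would have no eligible responses.

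**Cost.** The first option adds staff contact time at baseline and follow-up. The second may slightly lower completion in months 6-12, and a missed questionnaire would also lose that week's tablet count. The analysis additions need no new data.
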